5.5 Women of Childbearing Potential

Women of childbearing potential (WOCBP) include any female who has experienced menarche and who has not undergone successful surgical sterilization (hysterectomy, bilateral tubal ligation, or bilateral oophorectomy) or is not postmenopausal. Post menopause is defined as:

1. Amenorrhea greater than or equal to 12 consecutive months without another cause and a documented serum follicle stimulating hormone (FSH) level > 35mIU/mL or
2. Woman with irregular menstrual periods and a documented serum follicle stimulating hormone (FSH) level > 35mIU/mL or

NOTE: FSH level testing is not required for women greater than or equal to 62 years old with amenorrhea of greater than or equal to one year

3. Woman on hormone replacement therapy (HRT)

Women of childbearing potential (WOCBP) and men must be using two acceptable methods of contraception to avoid pregnancy throughout the study and for up to 56 days after the last dose

of investigational product in such a manner that risk of pregnancy is minimized. It is required that all WOCBP use two methods of contraception for the duration of the study (i.e. beginning before treatment with the 1 dose of study medication to 56 days after dosing). The two methods should include one barrier method (ex. condom with spermicidal gel, intrauterine devices, cervical cap etc.) and one other method. The other method could include oral contraceptives or another barrier method (Note an Intra Uterine Device is considered one method).

Women who suspect that they have become or may have become pregnant despite using proper birth control methods, should use the home pregnancy test provided at Baseline Visit. Home pregnancy test should be administered prior to taking Investigational Study Drug. Patient should not take Investigational Study Drug if they are pregnant and patient should immediately contact Study Investigator.

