4.2 Study Schematic

4.3 Schedule of Assessments

Table 1: Schedule of Assessments

Procedure	Screening Visit (3-28 days)¹	Baseline Visit (Randomization)¹	Onset of moderate or severe migraine²	During Treatment 15, 30, 45, 60 and 90 minutes Post-Dose	During Treatment 2, 3, 4, 6, 8 hours Post- Dose	During Treatment 24 hours Post-Dose	During Treatment 48 hours Post- Dose	End of Treatment Visit
Eligibility Assessments								
Informed Consent	X							
Inclusion/Exclusion Criteria	X	X						
Medical History	X							
Prophylactic Migraine Medication/ Concomitant Medication ³	X	X						X
Assessment of Migraine History (Signs and symptoms) paper source ¹⁴	X							
Safety Assessments								
Physical Examination	X							X
Vital Signs/Physical Measurements ⁴	X	X						X
Clinical Safety Laboratory Testing ⁵	X							X

Procedure	Screening Visit (3-28 days)¹	Baseline Visit (Randomization)¹	Onset of moderate or severe migraine²	During Treatment 15, 30, 45, 60 and 90 minutes Post-Dose	During Treatment 2, 3, 4, 6, 8 hours Post-Dose	During Treatment 24 hours Post-Dose	During Treatment 48 hours Post-Dose	End of Treatment Visit
ECG	X							X
Pregnancy Test ⁶	X	X	X					X
Adverse Event and Serious Adverse Event Assessment ⁷	X	X	X	X	X	X	X	X
Sheehan Suicidality Tracking Scale ⁸	X	X						X
Clinical Drug Supplies/Study Supplies								
Randomize ⁹		X						
Dispense Study Medication		X						
Administer 1 dose of study medication ¹⁰			X					
Return unused study medication								X
eDiary returned/reviewed for completeness ¹¹								X
Efficacy Assessments¹²								
Assessment of migraine pain ¹³			X	X	X	X	X	

Procedure	Screening Visit (3-28 days)¹	Baseline Visit (Randomization)¹	Onset of moderate or severe migraine²	During Treatment 15, 30, 45, 60 and 90 minutes Post-Dose	During Treatment 2, 3, 4, 6, 8 hours Post-Dose	During Treatment 24 hours Post-Dose	During Treatment 48 hours Post-Dose	End of Treatment Visit
Assessment of Migraine Symptoms (photophobia, phonophobia, and nausea - eDiary) ¹³			X	X	X	X	X	
Functional Disability Scale ¹³			X	X	X	X	X	
MQoLQ (Migraine Specified Quality of Life Questionnaire) ¹³						X		
Preference of Medication ¹³						X		

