¹ **Screening/Baseline Phase** will be 3 - 28 days. The **Baseline Visit** may be scheduled but should only occur *after* all screening procedures are complete, patient meets inclusion/exclusion criteria, and lab test results have been received by the site.

² Patients will use eDiary to answer questions about their migraine symptoms upon experiencing a moderate/severe migraine headache. The patient will administer pre-dispensed study drug if 1) the headache remains moderate or severe; 2) the patient has completed all required migraine assessment questions in the eDiary, including their current most bothersome migraine symptom, and 3) the patient has not already taken prohibited medications (see protocol section 5.4).

³ Patients should keep track of their concomitant medications throughout the study and report them to the study personnel at the End of Treatment Visit. Any medication taken for recurrent headache should be documented. Use of concomitant medications after randomization, including rescue medications, will be recorded by the patient on a paper diary and reported to the site.

⁴ Height will only be captured at the Screening Visit. Weight body temperature, respiratory rate, blood pressure and heart rate will be collected at all time points where indicated. Sitting arterial systolic and diastolic blood pressure and pulse rate will be measured.

⁵ All Screening Visit laboratory test results must be received prior to Baseline Visit.

⁶ A serum pregnancy test will be completed at Screening and End of Treatment Visits as part of the standard laboratory tests (if appropriate). Confirmatory urine pregnancy test for WOCBP should be completed on site at Baseline Visit and any subsequent visits for confirmation at the Investigator's discretion. Home pregnancy test will be provided to WOCBP after completion of baseline visit.

⁷ SAEs are reported from the time of informed consent and non-serious AEs are reported from baseline. All ongoing non-serious AEs and SAEs will be followed to resolution or until investigator deems there will be no further status change. SAE and AE's that occur during the treatment period should be reported to the site.

⁸ This scale will be clinician administered, completed on site, and will be in paper. The source document will be provided by Biohaven. The assessment period for completing the scale will be 30 days prior to Screening, and since the last visit for the remainder of the study.

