6.2.4 Laboratory Assessments

6.2.4.1 Safety Laboratory Testing

Blood and urine samples will be obtained as outlined in [Table 1](#) for clinical laboratory evaluations. A central laboratory vendor will be utilized for this study and a laboratory manual will be provided to each site. **If possible, patients should be fasting for a minimum of 8 hours prior to all blood draws.** However, if a patient is not fasting at a given visit, the blood draw should still be performed, and the non-fasting status should be documented.

Hematology: Hemoglobin, hematocrit, red blood cell count, white blood cell count (WBC) with differential, and platelets

Blood chemistry/electrolyte: Sodium, potassium, chloride, bicarbonate, calcium; glucose, BUN (urea), serum creatinine, uric acid, ALT, AST, alkaline phosphatase, LDH, total protein, albumin, total bilirubin, direct bilirubin, indirect bilirubin, CPK (with local lab fractionation, if central lab CK result is $> 1.5 \times \text{ULN}$);

Lipid panel: Cholesterol, LDL, HDL, triglycerides (Screening Only).

Estimated glomerular filtration rate: eGFR using the estimated MDRD formula will be calculated and reported by the central lab at each visit that clinical laboratory tests are collected as outlined in [Table 1](#).

Urinalysis: pH, specific gravity, ketones, nitrites, urobilinogen, leukocyte esterase, protein, glucose and blood. If blood, protein or leukocytes are positive, reflex to microscopic examination.

Urine Drug Screen: For drugs of abuse

6.2.4.2 *Pregnancy Testing*

Pregnancy tests will be conducted (serum, urine, or home pregnancy test), if appropriate prior to randomization, and as outlined in [Table 1](#).

6.2.5 **Sheehan Suicide Tracking Scale**

The Sheehan STS is a prospective, patient self-reported or clinician administered rating scale that contains 16 questions to track both treatment-emergent suicidal ideation and behaviors [16, 17]. If the investigator determines that a subject is at risk of suicide or self-harm, appropriate measures to ensure the subject's safety and obtain mental health evaluation must be implemented. The subject must immediately be discontinued from the study. The event should be recorded as either an AE or SAE as determined by the investigator and reported within 24 hours to the Sponsor.

6.3 **Efficacy Assessments**

6.3.1 **Pain**

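### Table 1 schedules a pregnancy test at onset of the treated migraine, but section 5.5 can be read as limiting it to women who suspect pregnancy, and the numbered dosing conditions omit it

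*Protocol*

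**What the plan says.** Several texts point to a test by every WOCBP before dosing:

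- Protocol Table 1 has a row "Pregnancy Test" marked at Screening, Baseline, onset of the moderate or severe migraine, and End of Treatment.
- Section 6.2.4.2: "Pregnancy tests will be conducted (serum, urine, or home pregnancy test), if appropriate prior to randomization, and as outlined in" Table 1.
- Table 1 footnote 6: "Home pregnancy test will be provided to WOCBP after completion of baseline visit". The supply is not limited to women who suspect pregnancy. The footnote assigns serum tests to Screening and End of Treatment and a urine test to Baseline. It does not say which test answers the onset mark.

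Section 5.5 has three relevant sentences. The first is "Women who suspect that they have become or may have become pregnant despite using proper birth control methods, should use the home pregnancy test". The second is "Home pregnancy test should be administered prior to taking Investigational Study Drug", with no group named. The third begins "Patient should not take Investigational Study Drug if they are pregnant".

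Table 1 footnote 2 sets the conditions for dosing. It starts with "The patient will administer pre-dispensed study drug if 1) the headache remains moderate or severe", then requires the eDiary questions, including the most bothersome symptom, to be completed, and ends with "3) the patient has not already taken prohibited medications". There is no fourth condition.

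**The concern.** Dosing happens at home with no site staff present, so the written instruction is the control. Section 5.5 bars dosing in pregnancy, and exclusion 4b covers a positive test before study drug, but neither protects a woman who does not suspect pregnancy unless she tests. The study gives one dose. The response in section 8.1.4, stopping the product, cannot undo a dose already taken.

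Sites are left with a practical problem too. If a WOCBP doses without testing, Table 1 suggests a deviation and the narrow reading of 5.5 suggests none, so section 5.7 cannot be applied uniformly.

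**Working it through.** **Text check.** The plan states no figure on this point, so the first step is to compare what each text asks of a WOCBP who does not suspect pregnancy.

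| Protocol text | Test before dosing? |
|---|---|
| Table 1, onset column | Yes |
| 6.2.4.2 | Yes, by reference to Table 1 |
| Footnote 6 | Kit supplied; use at onset not stated |
| 5.5, first sentence | No, suspicion only |
| 5.5, second sentence | Yes if it covers all WOCBP; no if it only times the suspicion-based test |
| Footnote 2 | Not among the three conditions |
| Footnote 10, synopsis, 1.4.1, 4.3.2, 7.2.2, 7.4 | Not mentioned |

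SAP section 2.1 also describes when to dose and does not mention the test. Two of these texts require the test, one can be read either way, and the instructions a patient would follow at the moment of dosing leave it out.

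**Time since the last required test.** Inclusion 3d requires a negative test at Baseline before drug is dispensed. Section 4.3.4 withdraws patients with no qualifying migraine within 45 days of randomization. The gap from that test to the dose therefore runs from 0 to 45 days.

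To show how the gap is spread, assume that attacks occur at random (Poisson) over a 30-day month, that the first qualifying attack is treated, and that the woman doses within 45 days. Inclusion 2c and 2e set limits of 8 and 2 moderate or severe attacks a month; 4 a month is added as an assumed middle value. With r attacks a month:

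- daily rate λ = r/30
- no attack in 45 days: p = exp(−45λ)
- mean gap among dosed women = 1/λ − 45p/(1 − p)
- share of dosed women with gap over t days = (exp(−λt) − p)/(1 − p)

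For r = 2: λ = 0.0667 and p = exp(−3) = 0.0498. Mean = 15 − 45 × 0.0498/0.9502 = 12.6 days. Over 14 days: (0.3932 − 0.0498)/0.9502 = 36%. Over 28 days: (0.1546 − 0.0498)/0.9502 = 11%.

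| Attacks per month | No attack in 45 days | Mean gap (days) | Over 14 days | Over 28 days |
|---|---|---|---|---|
| 2 | 5.0% | 12.6 | 36% | 11% |
| 4 | 0.25% | 7.4 | 15% | 2.1% |
| 8 | under 0.001% | 3.7 | 2.4% | 0.06% |

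The first row is an extreme. Inclusion 2e asks for at least 2 such attacks in each of 3 months. A woman averaging exactly 2 would meet that with probability (1 − 3e^−2)^3 = 0.594^3 = 21% under the same model.

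**The case against.** The strongest reply is that the test is already planned. Table 1 marks it, 6.2.4.2 makes the table binding, the kit goes to WOCBP without restriction, and the second home-test sentence of 5.5 carries no suspicion qualifier. Footnote 2 is attached to the same onset column that carries the test mark, and it does not say that its conditions are exhaustive or override the schedule. General dosing text need not repeat a rule for one subgroup.

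Most of this stands, and it is why a test by every WOCBP is the better reading. A reader might infer that the protocol contradicts itself or never calls for a test at onset. The documents do not support that: 5.5 is ambiguous, not contradictory. What the reply leaves open is that a numbered list of conditions for taking the drug is easily read as complete, and that a sentence placed straight after a suspicion-based instruction is easily read as continuing it.

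Two further points stand. What women are told at onset through eDiary prompts, kit instructions or the consent form cannot be seen here, and it may already settle the matter in practice. And if the sponsor does intend testing on suspicion only, qualifying the onset mark in Table 1 would also make the protocol consistent, though it would leave unsuspected pregnancies untested.

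**Conclusion.** This is a wording inconsistency on a participant-safety step, worth a cheap correction. As written, a WOCBP with an unsuspected pregnancy could follow the dosing text exactly and dose untested, at most 45 days after the Baseline test.

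The absolute risk is small: a serum test at Screening, a test at Baseline, two contraceptive methods and a single dose. It cannot be quantified, because the documents give neither the number of WOCBP nor a pregnancy rate. A reader might take the 36% or 11% in the first row as a share of women at risk of exposure. They are only times since the last required negative test, at the lowest permitted attack rate and under the random-attack assumption. The conclusion itself rests on the text comparison and would stand without the model.

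The estimands, power and type I error are not affected.

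**What to change.** 1. In 5.5, keep the test-on-suspicion sentence and replace the second home-test sentence with: *Every WOCBP must take the home pregnancy test at onset of the migraine to be treated, before the pre-dose eDiary questions, whether or not she suspects pregnancy, and must not take study drug unless the result is negative.* Testing before the eDiary questions keeps the baseline ratings next to the dose.
2. In Table 1 footnote 2, add: *and 4) for WOCBP, the home pregnancy test is negative.*
3. In footnote 6, state that the home test is the onset test marked in Table 1.
4. In footnote 10, the synopsis, 1.4.1, 4.3.2, 7.2.2 and 7.4, a cross-reference to 5.5 is enough. Changing the copy of the footnotes in SAP Appendix 2 is optional, since the SAP does not direct patients.

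Cost: the test is already scheduled and home kits are already supplied, so no new procedure is needed. There is a short delay before dosing during an attack. The number of kits per woman is not stated, so a woman who used hers on suspicion, or had an invalid result, needs a second or replacement kit. A few women may go undosed if no valid test is at hand. They would fall outside the mITT population, whose definition does not change. The test comes before a blinded dose, so there is no reason to expect those losses to differ by arm.

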5.6 Other Restrictions and Precautions (if applicable)

Not Applicable

5.7 Deviation from Inclusion/Exclusion Criteria

Any significant event that does not comply with the inclusion exclusion criteria, study conduct, or study procedures will be documented as a deviation. Deviations will be documented and reported through the clinical monitoring of the trial. Deviations will be reported to the IRB/EC at the frequency required by your IRB/EC. There will be no protocol exceptions granted by the Sponsor for Inclusion/Exclusion criteria.

6 STUDY CONDUCT AND DESCRIPTION OF STUDY PROCEDURES

6.1 Study Materials

The following study materials will be provided at the study start:

- Investigator File/Regulatory Binder
- Pharmacy Binder
- Drug Accountability Logs
- Sample source documents, where applicable
- Concomitant and Rescue Medication Logs (take home for patient)
- Investigator Brochure
- Interactive Web-based Response System (IWRS)
- Electronic Case Report Form (eCRF) instructions
- Electronic Diary (eDiary): 1 will be given to each randomized patient
- Instructions for the ePRO device and access to the portal
- Laboratory Kits and Laboratory Manual
- Home Pregnancy Test
- ECG Machine and Instructions
- Serious Adverse Event (SAE) forms
- Pregnancy Surveillance Forms

All sites will use an Electronic Data Capture (EDC) tool to submit study data to Sponsors CRO. Electronic Case Report Forms (eCRFs) will be prepared for all data collection fields including Serious Adverse Events (SAE) Reporting. SAE data (including responses to queries) will be submitted to the CRO using eCRFs. Electronic Patient Reported Outcomes (ePRO) will be used for all patient-rated scales and will be captured on an eDiary. Any assessment completed by the patient in the eDiary will be transferred from the site/patient to the vendor and from the vendor to the CRO and/or sponsor. No additional source documents are required for scales and assessments completed by the patient in eDiary.

Safety laboratory, plasma, serum, instructions for all specimens collected will be provided by a designated central laboratory. ECG equipment, supplies, instructions and training materials will be supplied by a centralized ECG vendor.

6.2 Safety Assessments

6.2.1 Vital Signs and Physical Measurements (Height and Weight)

Body weight and height will be recorded at the scheduled visits as outlined in [Table 1](#).

6.2.2 Electrocardiogram (ECG)

A standard 12-lead ECG will be recorded during the Screening Phase and at all scheduled visits as outlined in [Table 1](#). A central ECG service will be utilized for all ECGs and the investigator will determine if any abnormalities are clinically significant or not.

6.2.3 Physical Exam

Patients will undergo a routine physical examination during the Screening Phase and at all scheduled visits as outlined in [Table 1](#).

6.2.4 Laboratory Assessments

6.2.4.1 Safety Laboratory Testing

Blood and urine samples will be obtained as outlined in [Table 1](#) for clinical laboratory evaluations. A central laboratory vendor will be utilized for this study and a laboratory manual will be provided to each site. **If possible, patients should be fasting for a minimum of 8 hours prior to all blood draws.** However, if a patient is not fasting at a given visit, the blood draw should still be performed, and the non-fasting status should be documented.

Hematology: Hemoglobin, hematocrit, red blood cell count, white blood cell count (WBC) with differential, and platelets

Blood chemistry/electrolyte: Sodium, potassium, chloride, bicarbonate, calcium; glucose, BUN (urea), serum creatinine, uric acid, ALT, AST, alkaline phosphatase, LDH, total protein, albumin, total bilirubin, direct bilirubin, indirect bilirubin, CPK (with local lab fractionation, if central lab CK result is $> 1.5 \times \text{ULN}$);

Lipid panel: Cholesterol, LDL, HDL, triglycerides (Screening Only).

Estimated glomerular filtration rate: eGFR using the estimated MDRD formula will be calculated and reported by the central lab at each visit that clinical laboratory tests are collected as outlined in [Table 1](#).

Urinalysis: pH, specific gravity, ketones, nitrites, urobilinogen, leukocyte esterase, protein, glucose and blood. If blood, protein or leukocytes are positive, reflex to microscopic examination.

Urine Drug Screen: For drugs of abuse

6.2.4.2 *Pregnancy Testing*

Pregnancy tests will be conducted (serum, urine, or home pregnancy test), if appropriate prior to randomization, and as outlined in [Table 1](#).

6.2.5 **Sheehan Suicide Tracking Scale**

The Sheehan STS is a prospective, patient self-reported or clinician administered rating scale that contains 16 questions to track both treatment-emergent suicidal ideation and behaviors [16, 17]. If the investigator determines that a subject is at risk of suicide or self-harm, appropriate measures to ensure the subject's safety and obtain mental health evaluation must be implemented. The subject must immediately be discontinued from the study. The event should be recorded as either an AE or SAE as determined by the investigator and reported within 24 hours to the Sponsor.

6.3 **Efficacy Assessments**

6.3.1 **Pain**

Subjects are given an eDiary to record their migraine pain score, on a 4-point numeric rating [no pain, mild pain, moderate pain, severe pain] at the time points indicated in [Table 1](#).

6.3.2 Nausea, Phonophobia and Photophobia

The migraine associated symptoms of photophobia, phonophobia and nausea are measured on a two point scale (present or absent), using the eDiary, at the time points listed in [Table 1](#). If a subject reports the presence of a symptom, the subject is then asked to rate the severity of the symptom on a four point scale (none, mild, moderate or severe). All assessment is done using the eDiary.

The subjects are also asked to identify their most bothersome symptom on the eDiary (nausea, phonophobia or photophobia) at the onset of the migraine to be treated. The most bothersome symptom must be identified before the subject takes study medication.

6.3.3 Rescue Medication

The subject's use of rescue medication is recorded by the subject in a paper diary.

6.3.4 Functional Disability

Impact of treatment on functional disability will be assessed using a single-question scale. Subjects rate the level of disability they perceive as a result of their migraine in performing normal actions. This is done in the eDiary, at the times indicated in [Table 1](#), using a 4 point numeric rating scale: Normal Function, Mild Impairment, Severe Impairment, Required Bedrest.

6.3.5 Migraine Quality of Life Questionnaire

Impact of treatment on subject-reported quality of life will be assessed using The Migraine Quality of Life Questionnaire (MQoLQ). The MQoLQ is a 15-item instrument that has been validated in migraine patients to measure the short-term impact of treatment (within 24-hours) on seven migraine-specific domains: work, social function, energy, vitality, feelings, concerns, and migraine symptoms. The eDiary is used to evaluate the Migraine Quality of Life Questionnaire at 24 hours post-dose (see [Table 1](#)).

